3.4 Primary Safety Endpoints

We will monitor for adverse events occurring during 12 weeks of curcumin treatment as part of this study. In addition, occurrence of any of the following will be considered a treatment failure:

- Deterioration of liver biochemistries (doubling of bilirubin and/or increase in AST, ALT, and alkaline phosphatase levels $\geq 3x$ upper limit of normal or baseline levels without mechanical obstruction)
- Voluntary drug/study discontinuation for any reason (e.g. worsening of fatigue or pruritus or development of diarrhea, headache, nausea, or rash)
- Death
- Liver transplantation

4 Subject Selection Enrollment and Withdrawal

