4.1 Inclusion Criteria

Inclusion criteria will be as follows:

- Diagnosis of PSC established by all of the following criteria:^{27, 43}
 - ALK $>1.5x$ upper limit of normal for at least 6 months prior to study enrollment

- Cholangiography demonstrating intrahepatic and/or extrahepatic biliary dilation, beading, and/or strictures consistent with PSC
- Age 18-75 years
- Male or female sex
- Women of child-bearing potential willing to use birth control for the duration of the study
- Informed consent provided by the patient for study participation

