5.9.3 Dispensing of Study Drug

A 12 week supply of the study drug will be assigned and dispensed to each study participant. Drug reconciliation checks will be performed by the study team and documented in the medical record. Subjects will be requested to mail in any unused study drug if unable to return for the 12 week visit.

Return or Destruction of Study Drug

At the completion of the study, there will be a final reconciliation of drug shipped, drug dispensed, drug returns, and drug remaining. This reconciliation will be documented in the study file. Study drug destroyed on site per Mayo Pharmacy policy.

6 Study Procedures

Study procedures are summarized in section 3.1 as well as in Table 1.

Screening Visit (-28 to Day 0)

Screening assessments will be completed within 28 days of the baseline/Day 1 visit.

The following procedures will be performed and documented:

- Obtain signed informed consent
- Determine inclusion eligibility
- Obtain medical history
- Perform complete physical examination
- Obtain body height and weight
- Obtain vital signs (resting blood pressure, pulse, respiratory rate and temperature)
- Obtain details of concomitant medications
- Obtain blood samples for
 - Alkaline phosphatase
 - AST

ALT
Total bilirubin
C-reactive protein
Complete blood count (CBC)
INR
Sodium
Creatinine
Albumin
Stored serum
Serum pregnancy test for females of childbearing potential only
Questionnaires
Health status
Pruritus
Fatigue

Subjects meeting all of the inclusion criteria and none of the exclusion criteria will return to the clinic for the Baseline/Day 1 visit.

Treatment Assessments

Baseline/Day 1 Visit

Dispense study medication
Instruct the subject on the packaging, storage and administration of the study drug
If indicated, observe the subject take the first dose of the study drug

Week 3 (+- 7 days)

Obtain blood samples for
Alkaline phosphatase
AST
Total bilirubin
C-reactive protein
Complete blood count (CBC)
Creatinine
Albumin

Phone call or visit to assess for AEs, concomitant medications, and study drug compliance. Note a local laboratory can be used for obtaining the blood samples if subject is unable to return to Mayo.

Week 8 (+- 7 days)

Phone call to assess for AEs, concomitant medications, and study drug compliance. Note a local laboratory can be used for obtaining the blood samples if subject is unable to return to Mayo.

Week 12 (+- 7 days) or Early Termination

Obtain blood samples for
 Alkaline phosphatase
 AST
 ALT

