7.3 Subject Population(s) for Analysis

The study participants whose data will be subjected to data analysis include:

- All-treated population: Any subject entered into the study that received at least one dose of study drug.
- All-completed population: Only subjects who completed all study related procedures and follow-up will be included

8 Safety and Adverse Events

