8.1 Adverse events and study discontinuation

Patients will be discontinued from the study if they: 1) request withdrawal from the study, 2) develop worsening of underlying liver function defined as doubling of serum total bilirubin and/or increase in ALK or AST to $\geq 3x$ the upper limit of normal or baseline levels without mechanical biliary obstruction, 3) have side effects to study drug (e.g. diarrhea) that are not controlled by over the counter medication (e.g. loperamide), or 4) experience an adverse event based on CTCAE 4.0 criteria of grade 3 or higher that is not related to underlying disease.

When an adverse event has been identified, the study team will take appropriated action necessary to protect the study participant and then complete the Study Adverse Event Worksheet and log. The investigators will evaluate the event and determine the necessary follow-up and reporting required (see next section).

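### Sections 3.4 and 8.1 do not say whether 3x ULN or 3x baseline defines deterioration; because everyone enters with raised ALK, a small rise can force discontinuation, and the two enzyme lists differ

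*Combined protocol and SAP*

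**What the plan says.** Section 3.4 counts deterioration of liver biochemistries as treatment failure: a doubling of bilirubin and/or an "increase in AST, ALT, and alkaline phosphatase levels" to 3 times or more the "upper limit of normal or baseline levels without mechanical obstruction". Section 4.4.1 withdraws any patient who meets 3.4.

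Section 8.1 discontinues a patient for a doubling of bilirubin and/or an "increase in ALK or AST to" 3 times or more the "upper limit of normal or baseline levels without mechanical biliary obstruction".

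Neither section says which reference applies to which patient or test, and no other section does. Section 4.1 requires ALK more than 1.5 times the "upper limit of normal for at least 6 months prior to study enrollment"; neither 4.1 nor 4.2 sets an upper limit.

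In section 6 and Table 1, ALK and AST are drawn at entry, week 3 and week 12. ALT is drawn at entry and at the visit headed "Week 12 (+- 7 days) or Early Termination", but not at week 3.

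**The concern.** ALK is at once the entry criterion, the primary endpoint and a trigger for mandatory discontinuation. A limit tied to ULN suits a test that is normal at entry, but here ALK is raised in every patient by design. If the ULN limit governs, the room between entry and the stopping level shrinks as entry ALK rises, and near 3x ULN it falls within ordinary fluctuation.

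Patients could then be stopped at week 3 without real deterioration, and selectively those whose ALK happened to rise. A patient so stopped has no 12-week on-treatment value and leaves the all-completed population. Whether that patient is also a treatment failure depends on which section is followed. In a 15-patient study, each such case is one-fifteenth of the sample.

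**Working it through.** The plan gives no figure to reproduce on this point. The check is threshold arithmetic, followed by an illustration under stated assumptions.

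**Inputs.** Entry ALK *b*, in multiples of ULN, with *b* > 1.5 (4.1). Limits of 3x ULN and 3x baseline (3.4, 8.1). ALK is measured at week 3 and week 12 (section 6).

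**Step 1: which limit is lower.** The baseline limit is 3*b* > 3 × 1.5 = 4.5x ULN. The ULN limit is 3x ULN. So min(3, 3*b*) = 3 for every eligible patient. The two limits coincide only at *b* = 1, which is ineligible.

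**Step 2: rise needed to trigger.** Under the ULN limit it is 3/*b* − 1. Under the baseline limit it is 3 − 1 = 200% for everyone.

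| Entry ALK (x ULN) | Rise needed to reach 3x ULN | 3x baseline (x ULN) |
|---|---|---|
| 2.0 | 3/2.0 − 1 = 50% | 6.0 |
| 2.5 | 3/2.5 − 1 = 20% | 7.5 |
| 2.9 | 3/2.9 − 1 = 3.4% | 8.7 |
| 3.0 or more | already at or above the level | 9.0 or more |

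**Step 3: the last row has two readings.** If the rule is met by any increase that leaves ALK at or above 3x ULN, a patient entering at 3x or more meets it with any rise. If an increase *to* the level means crossing it, that patient cannot cross 3x ULN and only the baseline limit is left, a 200% rise. An unchanged or lower ALK does not trigger on either reading.

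**Step 4: could ordinary variation trigger it at week 3?** The documents give no within-patient variability, so a CV of 10% to 20% is assumed. Entry and week-3 values are taken as independent and log-normal around one unchanging level *b*. With σ = √ln(1 + CV²) and p = 1 − Φ(ln(3/*b*)/σ), the chance of a week-3 flag is p(1 − p) on the crossing reading and p(1 − p) + p²/2 on the any-rise reading. (This ignores the entry floor, which matters little at these levels.)

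| Underlying level | p, CV 10% to 20% | Crossing reading | Any-rise reading |
|---|---|---|---|
| 2.0x ULN | 0.000 to 0.020 | 0% to 2% | 0% to 2% |
| 2.5x ULN | 0.034 to 0.179 | 3% to 15% | 3% to 16% |
| 2.8x ULN | 0.245 to 0.364 | 18% to 23% | 21% to 30% |
| 3.0x ULN | 0.5 | 25% | 37.5% |

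So patients whose usual ALK lies a little below 3x ULN face an appreciable false-flag chance on both readings. Well above 3x ULN the readings part: on the any-rise reading the week-3 value exceeds the entry value half the time, so the chance is 50%; on the crossing reading it is close to zero.

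**Step 5: the enzyme lists side by side.** Under 8.1, ALK alone is enough and ALT is absent. Section 3.4 joins AST, ALT and ALK with *and*. If each test is judged separately, an ALK-only stop is also a treatment failure. If all three must rise, it is not, and the limb cannot be assessed at week 3 because ALT is not drawn then. The other discontinuation item in 3.4, "Voluntary drug/study discontinuation for any reason", does not cover a stop that 8.1 imposes.

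**The case against.** The best reply is that the authors meant the usual convention, baseline for tests raised at entry and ULN for the rest, and that investigators would apply it. Section 8.1 speaks of worsening liver function and excludes mechanical obstruction, which implies clinical assessment. That may be the intent, but the text does not state it, and a mandatory stop should not depend on a guess.

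A reader might infer that every patient entering at 3x ULN or more is discontinued for any rise. The documents do not establish that: the crossing reading is fair, and the 50% figure fails with it. The problem survives, though. On that reading a patient at 2.9x stops after a 3.4% rise while one at 3.1x needs a 200% rise to 9.3x ULN.

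Section 1.5 lists increased ALK among reported curcumin effects that resolved on dose reduction or stopping, so an early ALK stop can be deliberate caution. This stands, and it bears on the multiple chosen for ALK. It does not justify leaving the reference unstated.

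Reading 3.4's *and* as a plain list of separately judged tests is natural and would remove most of the conflict. It remains one of two readings, and 8.1 still omits ALT.

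The consequence is also bounded. The primary endpoint in 3.2 is not defined through 3.4. A stopped patient has an early-termination ALK and stays in the all-treated population ("Any subject entered into the study that received at least one dose of study drug"). A patient first flagged at week 12 loses no primary data.

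**Conclusion.** Wrong as written. The rule names two references without choosing. For ALK, the lower is always 3x ULN, given only that entry ALK exceeds 1.5x ULN. Under 8.1 that permits mandatory discontinuation for a 20% rise from 2.5x ULN or a 3.4% rise from 2.9x. For entry at 3x or more, the requirement is anything from any rise to a 200% rise, depending on the reading. The status of an ALK-only stop as treatment failure depends on how 3.4's *and* is read.

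The week-3 false-flag chances rest on an assumed CV and no true change in ALK. The documents give no entry ALK distribution, so the number of patients affected cannot be derived. A reader might infer that the success proportion is biased by a definite amount; the documents do not support any such figure. What can be said is that week-3 losses would fall selectively on patients whose ALK rose.

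**What to change.** 1. In both 3.4 and 8.1, state the reference: a test normal at entry is judged against ULN; a test above ULN at entry, which always includes ALK, is judged against the patient's own baseline.
2. Use one list in both sections: AST, ALT or ALK.
3. Add ALT to the existing week-3 draw so that the list can be assessed then.
4. Have the sponsor state the baseline multiple for ALK. The plan's own figure is 3x, which for entry at 4x ULN acts at 12x ULN. A lower multiple such as 2x (8x ULN in that patient) is an option given the reported ALK effect in 1.5. It equals 3x ULN at the entry floor (2 × 1.5), but it appears nowhere in the plan and is a clinical judgement.

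The cost is wording in two sections and one assay on an existing sample, with no new visit. The downside is that the ALK and AST triggers act later in patients with raised entry values: for ALK entry at 2.5x ULN, a 200% rise at 3x baseline or 100% at 2x, instead of 20%. The bilirubin-doubling rule and the grade 3 or higher withdrawal rule in 4.4.1 remain. The corresponding grade rule in 8.1 is a weaker backstop because it excludes events related to the underlying disease.

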4.1 Inclusion Criteria

Inclusion criteria will be as follows:

- Diagnosis of PSC established by all of the following criteria:^{27, 43}
 - ALK $>1.5x$ upper limit of normal for at least 6 months prior to study enrollment

- Cholangiography demonstrating intrahepatic and/or extrahepatic biliary dilation, beading, and/or strictures consistent with PSC
- Age 18-75 years
- Male or female sex
- Women of child-bearing potential willing to use birth control for the duration of the study
- Informed consent provided by the patient for study participation

4.2 Exclusion Criteria

Exclusion criteria will be as follows:²⁷

- Treatment with any investigational agents within three months prior to or during the study.
- Known or suspected cholangiocarcinoma
- Untreated dominant stricture within past 3 months
- Suspected bacterial cholangitis within past 3 months
- Known decompensated cirrhosis.
- Uncontrolled inflammatory bowel disease defined by ongoing symptoms requiring escalation of medical therapy within past 3 months
- Treatment with systemic corticosteroids, colchicine, methotrexate, cyclosporine, chlorambucil, pentoxifylline, or tacrolimus, within three months prior to or during the study.
- Changes in Azulfidine, azathioprine, budesonide, or vitamin E therapies within three months prior to study enrollment.
- Treatment with systemic antibiotics within one month prior or during study.
- Concomitant treatment with NSAIDS, and anticoagulant warfarin.
- Changes in antiplatelet agents or antihyperlipidemics therapies within three months prior to study enrollment.
- Anticipated need for liver transplant within one year as determined by Mayo PSC risk score (<80% one-year survival without transplant)
- Active drug or alcohol use
- Findings suggestive of liver disease of an alternative or concomitant etiology, such as autoimmune hepatitis, chronic alcoholic liver disease, chronic hepatitis B or C infection, hemochromatosis, Wilson's disease, α 1-antitrypsin deficiency, non-alcoholic steatohepatitis, primary biliary cirrhosis, or secondary sclerosing cholangitis (e.g. post-LT biliary stricture)
- Pregnancy or lactation
- Extremes of age (younger than 18 or older than 75 years of age).
- Any condition that, in the opinion of the investigator, would interfere with the patient's ability to complete the study safely or successfully

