3.2 Primary Study Endpoints

The primary study endpoint in this study will be treatment success, as determined by the proportion of PSC patients who experience clinically significant improvement in Alkaline Phosphatase, as defined by: 1) a $\geq 40\%$ reduction in serum Alkaline Phosphatase (as compared to baseline value)³⁷ or 2) a decrease in serum Alkaline Phosphatase to less than 1.5 times the upper limit of normal following 12 weeks of curcumin treatment.³⁸

Notably, serum Alkaline Phosphatase values have been repeatedly associated with disease response and prognosis,³⁹⁻⁴¹ thus this readily measured biochemical test is an important endpoint and biomarker in studies of patients with PSC.

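### The dominant-stricture exclusion does not clearly cover recently treated strictures, and the primary endpoint has no rule for biliary intervention, so an ALK fall from relieved obstruction can be scored as curcumin success

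*Combined protocol and SAP*

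**What the plan says.** The entry criteria in 4.1 require ALK above 1.5 times the "upper limit of normal for at least 6 months prior to study enrollment". They do not ask for a stable value. Strictures on cholangiography are among the findings that establish the diagnosis.

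The exclusions in 4.2 include "Untreated dominant stricture within past 3 months" and, as the next item, "Suspected bacterial cholangitis within past 3 months". Two others could bear on recent procedures: "Treatment with systemic antibiotics within one month prior or during study" and "Any condition that, in the opinion of the investigator, would interfere with the patient's ability to complete the study safely or successfully". Section 5.6 lists drugs only. None of these sections names dilation, stenting or any other biliary procedure.

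The primary endpoint in 3.2 is met by a fall in ALK of at least 40% from baseline, or by "a decrease in serum Alkaline Phosphatase to less than 1.5 times the upper limit of normal following 12 weeks of curcumin treatment". In Section 6, blood is drawn at screening, up to 28 days before Day 1. No sample is listed for the Day 1 visit, and Table 1 has a single entry column, so the baseline ALK is the screening value.

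Mechanical obstruction is mentioned only in the rules on deterioration: "upper limit of normal or baseline levels without mechanical obstruction" in 3.4 and "baseline levels without mechanical biliary obstruction" in 8.1. There is one treatment group (5.3), and 7.1 compares it with a 5% spontaneous success rate.

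**The concern.** ALK in this disease responds to the state of the ducts. The protocol accepts this when it sets aside a worsening that is due to obstruction. A patient whose obstruction has just been relieved therefore has a reason, unrelated to curcumin, to show a falling ALK over the next 12 weeks. Such a patient can still satisfy the six-month ALK criterion, because the values were high while the duct was narrowed.

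In a randomised trial a control arm would absorb falls of this kind. Here there is none. The benchmark is a rate of spontaneous improvement, and improvement after drainage is not spontaneous. With 15 patients, each misattributed success adds 1/15 = 6.7 percentage points to the observed proportion, on which the decision about a larger trial rests.

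**Working it through.** **Step 1. The plan's own figures.** Inputs from 7.1: N = 15, null rate 5%, alternative 30%, two-sided 0.05, stated power about 90%, and a result of at least 30% regarded as promising. With X ~ Binomial(15, 0.05), the exact tails are P(X ≥ 3) = 0.0362, P(X ≥ 4) = 0.0055 and P(X ≥ 5) = 0.0006. Exact power at 30% is 0.873 for ≥3 and 0.703 for ≥4. Neither matches 90%; N = 20 with ≥4 gives 0.893. That mismatch is a separate matter. What matters here is that the plan does not fix the cut-off. A count of 3 is significant by the minimum-likelihood two-sided exact p-value (0.036), whereas 0.025 per tail needs 4. The 30% bar falls at 0.30 × 15 = 4.5, so 4/15 (26.7%) is below it and 5/15 (33.3%) is the first count above it. All three cut-offs are shown below.

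**Step 2. The two readings of the stricture bullet.** Reading A: a stricture present in the last 3 months that is still untreated. Reading B: a stricture that was untreated at any time in the last 3 months.

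| Situation | Reading A | Reading B |
|---|---|---|
| Stricture first opened shortly before screening | not excluded | excluded |
| Stricture first treated more than 3 months ago, procedure repeated shortly before screening | not excluded | not excluded |
| Repeat procedure on such a stricture between the screening ALK and Day 1 | no rule, no repeat ALK | no rule, no repeat ALK |
| Procedure during the 12 weeks | 3.2 silent | 3.2 silent |

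The choice of reading settles only the first row.

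**Step 3. Sensitivity of the false-positive chance.** Two inputs are assumptions, because the documents give neither: m, the number of such patients among the 15, and q, the chance that each meets the endpoint without a drug effect (range 0.3 to 0.8). The remaining 15 − m patients succeed at 5%, and outcomes are independent.

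For m = 1, with Y ~ Binomial(14, 0.05): P(≥r) = q·P(Y ≥ r−1) + (1−q)·P(Y ≥ r).
At r = 3, P(Y ≥ 2) = 0.1530 and P(Y ≥ 3) = 0.0300.
- q = 0.3: 0.3 × 0.1530 + 0.7 × 0.0300 = 0.067
- q = 0.8: 0.8 × 0.1530 + 0.2 × 0.0300 = 0.128

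For m = 2, with Z ~ Binomial(13, 0.05): P(≥r) = q²·P(Z ≥ r−2) + 2q(1−q)·P(Z ≥ r−1) + (1−q)²·P(Z ≥ r).
At r = 3 the three tails are 0.4867, 0.1354 and 0.0245.
- q = 0.3: 0.09 × 0.4867 + 0.42 × 0.1354 + 0.49 × 0.0245 = 0.113
- q = 0.8: 0.64 × 0.4867 + 0.32 × 0.1354 + 0.04 × 0.0245 = 0.356

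The same formulas at the other cut-offs give:

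| Cut-off | m = 0 | m = 1 (q 0.3 to 0.8) | m = 2 (q 0.3 to 0.8) |
|---|---|---|---|
| ≥3/15 | 3.6% | 6.7-12.8% | 11.3-35.6% |
| ≥4/15 | 0.5% | 1.2-2.5% | 2.4-9.5% |
| ≥5/15 | 0.06% | 0.2-0.3% | 0.4-1.7% |

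**Step 4. Shift in the expected proportion.** This is m(q − 0.05)/15. For m = 1 it runs from 0.25/15 = 1.7 to 0.75/15 = 5.0 percentage points; for m = 2, from 3.3 to 10.0 points.

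**The case against.** The best defence is that the bullet already does the job. A stricture opened last week was untreated within the last 3 months, so Reading B keeps the patient out. That reading matches the cholangitis item beside it and gives the 3-month window a purpose. It is a fair reading, so a reader who infers that every recently treated patient is eligible goes beyond the text. It does not reach the last three rows of the table in Step 2.

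Other exclusions may also stop some of these patients. The antibiotic item would catch a procedure covered by systemic antibiotics, including during the study, and the investigator may exclude at discretion. But the antibiotic item looks back one month only, the discretion clause concerns completing the study rather than confounding of ALK, and neither says how an affected patient is scored.

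A reader might also infer from 3.4 and 8.1 that the plan forgives mechanical change when it counts against the drug and credits it when it helps. The documents do not support this. Those are rules on safety failure and discontinuation. A patient whose ALK rises from obstruction is spared the failure label but is still not a success under 3.2, so the numerator gains nothing.

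Two further points stand. The documents do not say whether the historical series behind the 5% left out recently treated strictures; if it did not, part of the effect is already in the benchmark. And m and q are assumed: at the plan's own 30% bar the false-positive chance stays below 2% with up to two such patients.

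**Conclusion.** The gap is real and modest. The stricture bullet is ambiguous for a first treatment shortly before screening. On either reading it does not cover a repeat procedure, and 3.2 does not say how to count an ALK fall after an intervention between the baseline sample and week 12. With no control arm, any such fall that meets the endpoint is scored as curcumin success, and the success proportion is biased upward.

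The size cannot be derived from the documents. The larger figures apply only if 3/15 is taken as a positive result, and they depend on the assumed m and q, on independence, and on a 5% rate that contains none of this effect. They show sensitivity and are not estimates of actual bias. It would also be too strong to infer that one such patient decides the trial: moving from 4/15 to 5/15 requires exactly four other successes. The finding warrants a cheap clarification and does not undermine the design.

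**What to change.** Make two changes, both before any outcome data are seen.

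1. In 4.2, reword the bullet so that it excludes a dominant stricture that is untreated, or any biliary intervention (dilation, stent placement or removal), within a stated interval before the baseline ALK. The 3 months used in neighbouring bullets is an obvious candidate. The documents do not show that this is long enough for ALK to settle, so the sponsor should justify the interval chosen.
2. In 3.2, state that the baseline ALK is the screening value, and that a patient who has a biliary intervention between it and the week-12 ALK is not counted as a treatment success.

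The scheduled contacts in Section 6 ask about adverse events, concomitant medication and compliance, so biliary procedures need to be recorded there for the second rule to work.

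Both changes concern eligibility and scoring; neither affects whether or when a patient has a procedure. The cost is a short amendment. A few candidates wait longer to enter, and the scoring rule is conservative because it could discard a genuine response in a patient who also had an intervention.
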